6.4 Endpoint adjudication process

An end-point adjudication committee (EAC) will be appointed with the task of assessing the clinical data relating to all endpoints. Data collected from GPs, hospitals, specialists and other sources by the research staff will be presented to the EAC. The information available to the EAC will not only include the clinical source documentation obtained from the GP records but also death certificates and, if available, autopsy reports blinded to participant identity. The EAC will adjudicate through an online system with meetings conducted to resolve discordant adjudications and to develop decision rules.

7. Sub-studies and ancillary studies

7.1 STAREE-HEART

STAREE-HEART will conduct a suite of additional cardiac assessments in a subset of up to 500 STAREE participants before they are randomised to study medication. It aims to determine the effect of statin treatment over a 3 year period compared with placebo on markers of cardiac ageing. These include an echocardiogram which measures global longitudinal strain (GLS), which may predict incident atrial fibrillation (AF) and heart failure, and twice daily handheld ECG recordings over a 2-week period which may improve AF detection 4-fold compared to usual screening. Additionally, a new energy waveform 12-lead ECG will be performed. The assessments will take place prior to randomisation and will be repeated at the year 3 follow up.

7.2 STAREE-MIND

STAREE-MIND will conduct neuroimaging assessments in a subset of up to 300 STAREE participants. STAREE-MIND aims to determine the effect of statin treatment on longitudinal measures of brain health including grey matter volume, white matter integrity and white matter hyperintensities, cerebral perfusion and metabolism, and iron loading. It will also examine the relationship between imaging changes in the brain and cognitive impairment and dementia. The imaging will be conducted prior to commencement of the study medication and will be repeated at 4 years of follow up. The detailed STAREE MIND protocol is shown in appendix 10.

7.3 STAREE Healthy Ageing Biobank

Up to 2000 STAREE participants located near STAREE study sites with facilities for processing and storage of biospecimens (Melbourne, Perth and Hobart) will be invited to provide a blood and urine sample for the STAREE Healthy Ageing Biobank. This study aims to create a collection of biospecimens which can be used in future research to identify new biomarkers that are linked with development of clinical outcomes such as stroke, myocardial infarction, cancer and dementia.

8. Contingency plans for participant wellbeing

Participants will be advised to seek care from their usual treating GP (or other health care providers) for any medical condition arising during the course of the study. Any test measurement result that is outside the normal range will trigger a notification to the participant's GP.

Treating GPs will be co-investigators and provided with information about the study to aid the participant's involvement in the study (wherever possible).

8.1 Commencement of regular lipid lowering agents

A prescription for a lipid lowering agent will be reason to stop the study medication. The participant will cease study medication but continue in the study for observation (routine follow up visits).

8.2 Development of an indication for statins

Any participant who develops a recognised clinical indication (such as a myocardial infarction or stroke) for statin treatment may commence routine statin therapy. The participant will cease study medication but continue in the study for observation (routine follow up visits).

8.3 Post-trial care

At the end of the interventional phase of the trial, it is anticipated that participants will be followed passively for an additional 5 years, contingent on funding being obtained. During this period, study participants will continue to be treated by their usual GPs and follow up will be conducted annually by face to face or phone contact. Study participants will be asked to provide informed consent for the extended post-trial follow up.

9. Levels of participant involvement

9.1 Levels of participant involvement

The aim of the study is to assess outcomes on an intention to treat basis, i.e. to test the decision to prescribe a statin and the consequences of that decision. Therefore, every effort will be made to minimise loss to follow up with respect to determining mortality, dementia, disability and major adverse cardiovascular events. Loss to follow up will be minimised by recording three contacts for each participant including their GP, close relative living apart, and close friend.

Full participation in STAREE means that a participant is currently taking study medication and attending for study visits and/or phone calls. If participants request to change their level of involvement or withdraw from the study it will be explained to them that there are number of options. These may include the following:

Changes to study medication

Participants may decide to interrupt or discontinue the study medication for a number or reasons but regardless of this decision, they can continue to be active participants in STAREE:

On Medication: Participants are taking study medication (one or two tablets daily).

Medication interrupted: Participants have temporarily stopped taking study medication due to circumstances such as illness, injury or holidays or for other personal reasons. Participants who have interrupted their medication intend to re-start medication at a future date when the circumstances that have led to the interruption are resolved.

Medication discontinued: Participants have stopped taking study medication permanently. This may be due to adverse effects or for other personal reasons, or because they have developed a clinical indication and been prescribed an open label statin. In all cases, when a participant discontinues study medication, the reason for discontinuation and date of the last dose of study medication will be recorded

Participants who have stopped taking study medication and are deemed by a STAREE medical officer as suitable for medication re-challenge will also be considered as “interrupted” until they either re-start or are deemed to have permanently discontinued medication.

Changes to study visits (clinic and/or phone calls)

Regardless of whether participants are taking study medication or not, they will still participate in study visits (clinic and/or phone calls). If participants do not want to participate in study visits (clinic and/or phone calls), they may elect to participate by review of their medical records corresponding with the trial’s duration (such as GP and hospital records) and national morbidity and mortality databases). All participants will be asked to provide approval for access to this information as part of the study enrolment procedures.

9.2 Withdrawal

Participants will be considered to have withdrawn from the study if they revoke their consent. This means that they are not taking study medication, are not participating in study visits (clinic and/or phone calls), and that medical record review is not being conducted. All data that participants have contributed to the study up to the date of withdrawal will remain in the study database, and review of medical records dated earlier than the withdrawal date may be completed. Publicly available data such as death (e.g. from death notices) may also be used in such cases.

10. Study Medication and Supplies

10.1 Study treatments

Run-in placebo

The 4 week placebo medication will be provided in either a labelled box or bottle (one box or bottle of 40 tablets). It will be given to participants at the completion of baseline visit 1.

Double-blind Study Medication

Study medication will be provided by Ramsay Healthcare in boxed blister packs (3 sheets of 10 tablets), with the STAREE logo printed on the box. Participants will be randomly allocated to one of two treatments; a) atorvastatin (2 x 20 mg tablets) or b) placebo (2 x 20 mg tablets with identical appearance). Study medication will be posted regularly throughout follow-up, at least every 3-9 months (usually at 6-month intervals).

Post randomisation

After randomisation, study medication will be posted directly to the participant's home or provided to the participant at an annual visit. Participants will be directed to start taking one tablet of study medication from a labelled first box containing 30 tablets. Subsequently participants will be directed to take two tablets from boxes containing 30 tablets.

10.2 Administration of study medication

Run-in period

Participants will be directed to take 1 tablet of run-in medication at the same time every day.

Double blind period

Participants will be directed to take 1 tablet (20 mg) at the same time every day for the first 30 days of the trial. After 30 days, participants will be directed to take 2 tablets (40 mg) at the same time every day.

If a suspected intolerance of the full dose (2 tablets) of study medication (atorvastatin or placebo) develops, the participants' GP may reduce the dose to 1 tablet at their own discretion.

Administration of study medication for those taking allowed Cytochrome P450 3A4 inhibitor at study entry and during follow up

Participants identified as taking certain (allowed) cytochrome P450 3A4 inhibitors will be directed to take 1 tablet (20 mg) of study medication per day for the duration of the study. The list of allowed cytochrome P450 3A4 can be found in Appendix 3.

10.3 Dispensing and randomisation

The number of authorised dispensing staff will be limited to assure proper adherence with established accountability and dispensing procedures. All procedures are described in the STAREE Drug Accountability Manual.

Medication for the run-in phase will be dispensed to the participant by the study staff at baseline visit 1. Each participant will be dispensed 40 placebo tablets and be directed to take one tablet at the same time daily. When the participant returns for the final assessments and

eligibility visit (baseline visit 2), medication compliance will be checked prior to randomisation.

Following the completion of the randomisation process, study medication will be posted to the participant at regular intervals, as required, to ensure continuity of study medication supply for each participant. The participant will be asked to confirm receipt of the study medication by calling the STAREE coordinating centre. If confirmation of receipt has not been made within 10 days of dispatch of the study medication research, staff will contact the participant to ensure receipt. Attempts to contact the participant will continue until receipt has been confirmed. In the rare instance of missing or undelivered study medication, the study medication will be re-issued and sent to the home of the participant. Note, the postage of study medication to participants will be tracked with the delivery or courier service with the signature of the recipient being required upon delivery.

The Medication ID number assigned to the participant will remain the same for the duration of the study with each separate batch being distinguished by a batch number appended to the medication ID number. The participant will receive study medication with the same Medication ID number at each visit.

A 'Study Drug Log' will record the medication dispensed and the medication returned from the participant.

The *Study Drug Log* will record information on the dispensing of study drug and will include the following:

- Participant ID number and participant acrostic
- Medication ID number
- Date dispensed (initials of dispenser)
- Date of medication return (initialled by research staff)
- Number of tablets returned
- Comments section to allow for explanation of discrepancy, if applicable.

These processes are further detailed in the drug accountability manual.

10.4 Study medication compliance

Compliance with study medication will be checked at six-monthly telephone calls and annual visits. Questions regarding study medication use will also be asked at annual visits to encourage medication compliance (see Appendix 4). The questions are based on the Brief Medication Questionnaire⁶⁵ and Morisky questionnaire⁶⁶. Participants will be asked to count and report any unused tablets at annual visits.

10.5 Study medication storage

Study medication storage will be the responsibility of Ramsay Healthcare. Study medication will be predominantly stored at a secure storage centre in a temperature-controlled environment. Placebo run-in medication is released to STAREE periodically, in-bulk, and stored at the coordinating centre. All placebo medication for the run-in phase will be stored in a secured area with restricted access, at room temperature under the supervision of the coordinating centre.

The receipt, storage, dispensing, accountability and study medication collection, for both the run-in and randomisation phases, will be the responsibility of both Ramsay Healthcare and the STAREE coordinating centre. Each party will be responsible for maintaining appropriate delivery, storage, and transfer records.

10.6 Study medication accountability and dispensing logs

All study medication dispensed in the trial will be accounted for by confirming the delivery, receipt and commencement dates of each study medication supply. Study medication compliance will be assessed and confirmed by collection, counting and documentation of unused study medication from participants and/or by confirmation of the completion and/or cessation dates of each individual supply with participants by phone.

All unused study medication will be collected to allow for proper destruction of the medication. Unused tablets and packaging will be returned by participants to trial staff at face to face study visits. If unused study medication is not able to be collected at study visits, attempts will be made to confirm safe destruction (see section 8.7 below). Any lost medication packs will be documented, re-dispensed and posted to the participant, with all the details recorded to allow an audit trail. Tablet counts will be made of all returned medication packs. The coordinating centre will make all reasonable attempts to verify that any unused or partially used medication supplies are returned by the study participant and that no remaining supplies are in the participant's possession.

The coordinating centre will maintain records which adequately document that study participants were provided study medication supplies and doses as specified by the protocol and document and reconcile all study medication received from the participants (see section 8.3).

10.7 Study medication disposal

Unused study medication will be collected at annual visits by study staff whenever possible and disposed. Unused study medication will then be relinquished for safe destruction at a local pharmacy or destruction service. Each batch of destroyed study medication will be documented, along with the date, location and the pharmacy staff name, in the STAREE Study Medication Tracking Log (more detailed information is provided in the STAREE Drug Accountability Manual).

If unused study medication is not able to be collected at an annual study visit, participants will be given the option of disposing their supply at the local pharmacy (i.e. through the Return of Unwanted Medication or RUM scheme) or return via a reply-paid envelope satchel. Destruction of unused study medication by participants at pharmacies or other safe medical waste service will be documented on the STAREE Disposal Form, which will be returned to the STAREE trial for record keeping.

10.8 Overdose of study medication

There is no specific treatment for atorvastatin overdose. Should an overdose occur, the participant should seek emergency medical care and be treated symptomatically with

supportive measures instituted as required. The Poisons Information Centre on [name] (Australia) may also be contacted for advice on the management of an overdose.

11. Concomitant Therapy

11.1 Prescription medications

All prescription medicine will be recorded on a Concomitant Medications Form including indication for use and start/stop dates. Concomitant medications will be checked at annual study visits where participants will be asked to bring in any medications/vitamins/supplements they are taking and by review of GP medical records.

12. Sample Size and Power calculations

Table 4. Sample size calculations

	ITT effect size (RR)	Power	Required number of events	Required number of participants	On treatment (true) effect
For disability free survival (Death or Dementia or Disability)	14.5%	83.1%	1,397	9,631	18%
For major adverse cardiovascular events (CV death, non-fatal MI or non-fatal stroke)	20.2%	80.0%	619	9,631	25%

Based on these sample size calculations 9,631 participants will be recruited and a total of 58,135 person-years accrued.

These calculations assume:

Loss to follow up: 2% per annum (which is expected to be conservative, i.e. the true loss to follow up is expected to be very small assuming good retention of participants and the ability to access medical records or perform record linkage for those who cease regular follow up). This translates to expecting an average of 6.04 years of follow up time per participant.

A two-sided significance level of 5% (alpha rate).

An anticipated age structure of STAREE participants of 56%: 27%: 12%: 5% in the respective age bands 70-74 years: 75-79 years: 80-84 years: 85+ years. These proportions are based on recruitment of the initial 7000 participants to the study and expectations about future recruitment.

Treatment cross-over: In year 1 of follow up we assume 8% of participants who have been randomised to statin will cease taking their study medication. Thereafter, we assume 3% of participants per annum in the statin group will cease taking study medication. In year 1 of follow up we assume 1% of participants in the placebo group will commence statin. Thereafter we assume 3% of participants per annum in the placebo group will commence statin therapy. Further we assume that there are no subsequent treatment "re-cross-overs", i.e. assume a worst-case scenario for the hazard ratio that will be observed in the intention to treat analysis.

The following event rates:

Death, dementia or persistent disability (disability-free survival) - co-primary endpoint A

All cause death

We anticipate death rates in STAREE randomised participants will be less than half those in the general population. Specifically, the STAREE anticipated age-specific death rates are as follows:

70-74y	10.0 per 1000 person-years
75-79y	17.7 per 1000 person-years
80-84y	33.6 per 1000 person-years
85+y	66.6 per 1000 person-years

These event rates have been informed by corresponding mortality rates from the ASPREE (Aspirin in Reducing Events in the Elderly) randomised clinical trial and from underlying Australian population death rates for 2011, obtained from <http://www.abs.gov.au/AUSSTATS/abs@.nsf/DetailsPage/3302.02011?OpenDocument>

Dementia

Population rates of dementia have been estimated as 11 per 1000 person years in the 75-59 year old age group although fluctuations have been observed.⁶⁷⁻⁶⁹ For Australia, there is a paucity of national data to inform incidence rates, as noted by AIHW in 2012. The ASPREE trial provides a highly relevant contemporary source of information. A dementia rate of 6.8 per 1000 person years was observed in ASPREE (median age 74 years) although almost no cases occurred in the first year of follow up so the rate was higher in later years. In ASPREE, dementia was screened for using a 3MS reduction of at least 10 points and there was a 60% conversion of the screen-positives to confirmed cases of dementia. In STAREE a 3MS reduction of at least 5 points will be used, which is expected to approximately double the number of screen positives but lower the conversion rate to confirmed cases of dementia to 50%. From these considerations, 3MS screening in STAREE is expected to yield 33% more cases of dementia than in ASPREE. Given this, and detailed age-specific data from ASPREE, the dementia rates in the later years of follow up in STAREE are expected to be as follows, using participant age at randomisation:

70-74y	5.8 per 1000 person-years
75-79y	12.4 per 1000 person-years
80-84y	26.9 per 1000 person-years
85+y	36.6 per 1000 person-years

Physical Disability (defined as persistent loss of an activity of daily living)

This component is defined by a persistent “a lot of difficulty” or “unable to do the activity” rating, or “Yes” answer to receiving help to perform the same activity of daily living (ADL) domain/s (items 9 to 14), which is confirmed at least 6 months previously as loss of the same ADL. If it is not possible to obtain an ADL assessment, notification of admission to aged care or community assessment will initiate collection of relevant clinical records to substantiate a disability endpoint. The rate of this endpoint was negligible in the first year of ASPREE. The following rates are expected to be seen in later years of follow up in STAREE and are based on observed rates in ASPREE, using participant age at randomisation:

70-74y 4.5 per 1000 person-years
75-79y 7.6 per 1000 person-years
80-84y 12.5 per 1000 person-years
85+y 25.0 per 1000 person-years

Overlap of death, dementia and persistent physical disability

The overlap between these three components will be assumed to be 10%. This is consistent with the observed overlap between dementia and physical disability occurring prior to death in ASPREE. Hence the composite STAREE event rate is estimated to be the sum of the 3 component event rates less 10% of that sum.

The calculations of expected primary endpoint event rates in years 3-5 of follow up after randomisation are as follows:

[figure not shown]
70-74y: $(10.0 + 5.8 + 4.5) \times 0.9$ per 1000 person-years = 18.3 per 1000 person-years
75-79y: $(17.7 + 12.4 + 7.6) \times 0.9$ per 1000 person-years = 33.9 per 1000 person-years
80-84y: $(33.6 + 26.9 + 12.5) \times 0.9$ per 1000 person-years = 65.7 per 1000 person-years
85+y: $(66.6 + 36.6 + 25.0) \times 0.9$ per 1000 person-years = 115.4 per 1000 person-years

Consideration of healthy volunteer effect

It is anticipated that the event rates for disability-free survival calculated above will be reached by STAREE participants in years 3-5 following randomisation. In the initial 2 years of follow up participants are assumed to be healthy relative to the population, i.e. in the first 2 years of follow up STAREE participants are assumed to experience lower event rates. An event rate of 0 (zero) per 1000 person years is assumed in the first year of follow up for dementia and physical disability and a rate of 4 per 1000 person years is assumed for mortality. In the second year of follow up it is assumed that the primary endpoint event rate will be equal to half of that anticipated above in years 3-5.

Major adverse cardiovascular events (cardiovascular death, non-fatal myocardial infarction or non-fatal stroke) – co-primary endpoint B

This composite endpoint is defined as the first occurrence of cardiovascular death or non-fatal myocardial infarction or non-fatal stroke. In ASPREE this endpoint has been evaluated to the extent possible (of reported non-fatal myocardial infarction/angina events reported approximately 45% will be adjudicated as a non-fatal myocardial infarction). The figure below shows the estimated rate of major fatal and non-fatal cardiovascular events in ASPREE participants by age group. Of note, the underlying event rate seems fairly constant over the time from randomisation, i.e. the initial “healthy volunteer” effect that is seen in mortality and can be anticipated for admission to care, dementia and loss of activity of daily living, does not seem to apply to major adverse cardiovascular events. The three components, non-fatal myocardial infarction: non-fatal stroke: cardiovascular death, contribute events to the composite endpoint in the approximate ratio of 2:2:1 respectively.

Based on the rates seen in ASPREE the following rates are anticipated in STAREE:

Years 1-5:

70-74y	9.5 per 1000 person-years
75-79y	11.5 per 1000 person-years
80-84y	18.5 per 1000 person-years
85+y	24.5 per 1000 person-years

13. Safety Monitoring and Reporting

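### Table 4's disability-free survival effect (14.5%) and power (83.1%) fit an even time-average of cross-over; the plan's own event timing gives about 13.8% and 79%

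*Protocol*

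**What the plan says.** All inputs are in the protocol, Section 12 (Sample Size and Power calculations).

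- Table 4, row "For disability free survival (Death or Dementia or Disability": on-treatment effect 18%, ITT effect 14.5%, 1,397 events, power 83.1%.
- Table 4, row "For major adverse cardiovascular events (CV death, non-fatal MI or non-fatal stroke": on-treatment effect 25%, ITT effect 20.2%, 619 events, power 80.0%.
- Test level: "A two-sided significance level of 5% (alpha rate".
- Follow-up: "9,631 participants will be recruited and a total of 58,135 person-years accrued", a mean of 6.04 years, with "Loss to follow up: 2% per annum".
- Cross-over, statin arm: "In year 1 of follow up we assume 8% of participants who have been randomised to statin will cease taking their study medication", then 3% a year. Placebo arm: 1% start a statin in year 1, then 3% a year. Nobody crosses back.
- DFS timing: "An event rate of 0 (zero) per 1000 person years is assumed in the first year of follow up for dementia and physical disability", with mortality of 4 per 1000 person-years in that year. In year 2, "the primary endpoint event rate will be equal to half of that anticipated above in years 3-5".
- MACE timing: the rate is described as fairly constant from randomisation, and no early reduction is applied.

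The section does not say how 18% became 14.5% or how 25% became 20.2%.

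**The concern.** Cross-over only accumulates in this plan, so the contrast between arms weakens each year. A Cox hazard ratio reflects the contrast at the times when events occur. If events are spread evenly, an even average of cross-over over follow-up gives the right dilution. If events come late, it gives too little dilution.

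The plan applies its healthy-volunteer pattern to the DFS event rate. The DFS effect in Table 4 looks as if the same pattern was not carried into the dilution. The stated ITT effect and power for one of the two co-primary endpoints would then not follow from the plan's own inputs, and both would be somewhat optimistic. Someone judging whether DFS is adequately powered would rely on these two cells.

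**Working it through.** **Inputs.** The age mix is 56/27/12/5%. DFS rates for years 3–5 are 18.3, 33.9, 65.7 and 115.4 per 1000 person-years. The age-weighted rate is

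0.56×18.3 + 0.27×33.9 + 0.12×65.7 + 0.05×115.4 = 33.06 per 1000.

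Year 2 is half of this, 16.53, and year 1 is 4. The protocol gives the full rate for years 3–5; I assume that it continues into year 6. I take 1,397 events as stated (the rates and person-years give roughly 1,375–1,382).

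Cross-over at mid-year, accruing linearly:

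| Year | Off statin | Drop-in | DFS rate per 1000 | Share of DFS events |
|---|---|---|---|---|
| 1 | 4.0% | 0.5% | 4.00 | 2.6% |
| 2 | 9.5% | 2.5% | 16.53 | 10.8% |
| 3 | 12.5% | 5.5% | 33.06 | 21.6% |
| 4 | 15.5% | 8.5% | 33.06 | 21.6% |
| 5 | 18.5% | 11.5% | 33.06 | 21.6% |
| 6 | 21.5% | 14.5% | 33.06 | 21.6% |

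Years 3–6 hold 86.6% of DFS events here. With the 2% annual loss included the share is about 86%.

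**Formulas.** With on-treatment reduction d, off-statin share o and drop-in share p:

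- ITT hazard ratio = [1 − d(1 − o)] / [1 − d·p]
- Power = Φ(½·√events·|ln HR| − 1.96)

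**Reproducing Table 4 with equal weight per year.** o = 81.5/6 = 13.58% and p = 43/6 = 7.17%.

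- DFS: (1 − 0.18×0.8642)/(1 − 0.18×0.0717) = 0.8555. The effect is 14.45% (stated 14.5%). Power is Φ(2.917 − 1.96) = 83.1% (stated 83.1%).
- MACE: (1 − 0.25×0.8642)/(1 − 0.25×0.0717) = 0.7983. The effect is 20.17% (stated 20.2%). Power on 619 events is Φ(2.803 − 1.96) = 80.0% (stated 80.0%).

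One pair of averages matches all four figures.

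**Weighting by DFS event timing.** The weights are 4 : 16.53 : 33.06 × 4, which sum to 152.75.

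- o = (4×4 + 16.53×9.5 + 33.06×68)/152.75 = 15.85%, where 68 is the sum of the year 3–6 values.
- p = (4×0.5 + 16.53×2.5 + 33.06×40)/152.75 = 8.94%.
- HR = (1 − 0.18×0.8415)/(1 − 0.18×0.0894) = 0.8624, an effect of 13.76%.
- Power on 1,397 events = Φ(2.766 − 1.96) = 79.0%.

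Multiplying the weights by 2% annual loss gives 13.80% and 79.3%. For MACE the rate is constant, so event weighting leaves the effect at about 20.2%.

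**Sensitivity of the event-weighted result to details that the protocol leaves open.**

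| Cross-over timing | DFS effect | DFS power | MACE effect |
|---|---|---|---|
| Continuous, compounding, 6.44 planned years (mean about 6.04) | 13.8% | 79.4% | 20.2% |
| Continuous, linear, 6.44 years | 13.6% | 77.9% | 20.0% |
| Continuous, linear, 6 years | 13.8% | 79.3% | 20.3% |
| All at start of year, 6.44 years | 13.0–13.3% | 74–76% | 19.2–19.5% |
| All at end of year, 6.44 years | 14.1–14.3% | 81–82% | 20.7–20.9% |
| All at end of year, compounding, about 6 years | 14.4–14.6% | 83–84% | 21.1–21.3% |

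Removing participants from risk after their first event, with loss and continuous compounding, gives an event-weighted effect of 13.9% and power of about 80%. No event-weighted variant tried gives both 14.5% for DFS and 20.2% for MACE.

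**The case against.** The strongest objection is that the averaging method is inferred, because the protocol prints no derivation. The DFS row taken alone can be reached with event weighting: compounding cross-over, counted at the end of each year over about six years, gives about 14.5% and 83%. This stands as a caution. It does not rescue the table, because the same convention puts MACE at 21.1–21.3%, not the stated 20.2%.

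Second, within-year timing is not fixed in the protocol, and across all timings tried DFS power runs from about 74% to 84%. So 13.8% and 79% are not exact replacements. Requiring the MACE row to hold narrows the range to 13.6–13.9% and 78–80%.

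Third, the shift is small, about 0.7 points of effect and 3–5 points of power. The plan also calls its no-return assumption a worst case and its loss rate conservative. That is fair on importance. It does not make the two cells follow from the stated inputs.

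A reader might infer that DFS now has a miss rate above 20%. The documents do not support that firmly, since the plausible range reaches 80%. A reader might also infer that nearly all DFS events fall late. The plan's rates put about 86% in year 3 or later.

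**Conclusion.** The point holds as a modest inconsistency within Section 12. The DFS effect of 14.5% and power of 83.1% match an even time-average of cross-over, which suits the constant MACE rate but not the DFS rates in the same section. Weighted by the plan's own DFS timing, the effect is about 13.8% (13.6–13.9%) and power about 79% (78–80%) on 1,397 events.

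This rests on three assumptions: the years 3–5 rate continues into year 6, cross-over timing is such that MACE stays near 20.2%, and the event count is as stated. That even averaging was used is a strong inference, not something the protocol says.

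It would go too far to conclude that the trial is underpowered or needs more participants. DFS power stays close to 80%, and the MACE row, which is tested first under Section 14.3 (Data analysis), is unaffected.

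**What to change.** Recompute the DFS row of Table 4 with cross-over weighted by the expected timing of DFS events. Restate the ITT effect (about 13.8%) and power (about 79–80%). Add a sentence giving the cross-over timing convention (for example continuous accrual, linear or compounding), the follow-up length used, and the DFS rate assumed after year 5, so that both rows can be reproduced. Leave the MACE row and the 9,631 participants unchanged.

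The cost is two table cells and one sentence, and a slightly less favourable stated power for DFS.
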